1.3 Purpose, Usage and Target Audience of This Document

This document provides a detailed description of the analysis plan for the iPACK-HD trial. This document is meant to be used in conjunction with the study protocol. This document does not subsume the protocol, but several elements of the protocol, such as the sample size justification, are reproduced herein for completeness. This document has the following purposes:

1. Provides a written agreement between the Principal Investigator, lead study statistician and data analysts regarding exactly what analysis will be performed.
2. Provides a record of the analysis plan specified prior to unblinding treatment assignments that may be included as supplementary study documentation with the primary study publication.
3. Provides clear specifications for the analyst(s) performing the data filtering/transformation, variable derivations, statistical analyses, and report generation.

This document follows the guidance published in JAMA by Gamble et al (2017) and referenced at <https://www.equator-network.org/reporting-guidelines/guidelines-for-the-content-of-statistical-analysis-plans-in-clinical-trials/>.¹ The SAP checklist is completed in Appendix A.

3.1 Background and Rationale

Cardiovascular disease, which is due in part to progressive vascular calcification, is the leading cause of death among patients with end stage kidney disease (ESKD) on dialysis. A role for vitamin K in the prevention of vascular calcification is plausible based on the presence of vitamin K dependent proteins in vascular tissue, including matrix Gla protein (MGP). Evidence from animal models and observational studies support a role for vitamin K in the prevention of vascular calcification. A large-scale randomized controlled trial (RCT) is needed to investigate the effect of vitamin K supplementation on the progression of vascular calcification in patients with ESKD, a group at risk for sub-clinical vitamin K deficiency. But before undertaking a definitive large-scale RCT, a pilot study is required to assess the plausibility of the hypothesized intervention effect, and the feasibility of our group undertaking a large-scale RCT.

3.2 Overall Aim

The overall aim of this pilot trial is to assess feasibility and provide preliminary outcome results to support the design and funding application of a definitive phase II or III RCT to determine whether vitamin K treatment prevents coronary artery calcium (CAC) progression in hemodialysis (HD) patients.

3.3 Study Objectives

The **primary objective** of this trial is to pilot study procedures and assess the feasibility of implementing a larger scale definitive phase II or III trial assessing the same intervention in the same population as this trial.

The **secondary objective** of this trial is to explore the impact of vitamin K on CAC, clinical outcomes and vitamin K biomarkers.

The **tertiary objective** of this trial is to collect data that can be combined with the VitaVasK study to perform an individual patient data meta-analysis (IPD-MA). The IPD-MA is registered at PROSPERO (ID= 123104), and the analysis plan will be detailed in a separate document.

3.4 Study Hypotheses

We hypothesize that an adequately powered RCT to test whether vitamin K treatment inhibits the progression of CAC in patients with ESKD requiring HD treatment will be feasible (see section 7.1.1).

We hypothesize that vitamin K treatment will improve vitamin K biomarkers, reduce inflammation, prevent progression of CAC and valve calcification, reduce bone fracture, and improve body composition over 12 months.

4 Study Methods

4.1 Trial Design

The current iPACK-HD pilot trial is a prospective randomized parallel two-arm double-blind 3-centre feasibility and exploratory phase II trial in adults with ESKD requiring dialysis who have a baseline CAC score ≥ 30 Agatston units (AUs). Eligible patients were randomly assigned 1:1 to either the experimental treatment group (10 mg of phylloquinone thrice weekly) or to a control group (matching placebo thrice weekly). The initial plan was to roll patients from this pilot feasibility trial into a full definitive phase II RCT. However, due to pragmatic considerations including challenges obtaining Canadian Institutes of Health Research (CIHR) funding, this study is now a stand-alone pilot feasibility and exploratory phase II trial. If the results of this trial suggest that a large scale definitive RCT is warranted, then the feasibility and preliminary results will be used to help support the design and funding application for the definitive trial.

The protocol for the planned definitive RCT is published in the Canadian Journal of Kidney Health and Disease.² The protocol for this pilot feasibility trial is a successful grant application from the March 2015 CIHR RCT committee.

4.2 Randomization

Randomization was performed using web-based Central Randomization System (CRS) at the Clinical Evaluation Research Unit (CERU) at Kingston Health Sciences Centre (KHSC) - Kingston General Hospital (KGH) site. Randomization was concealed and stratified by site and diabetes mellitus using permuted blocks of random sizes disclosed as 2, 4 and 8 after enrollment completion. The prevalence of CAC is significantly higher in patients with diabetes mellitus; therefore, it was critical that the groups be balanced for this risk factor. Research Coordinators screened patients requiring HD. A de-identified log of screened patients was kept, recording inclusion and exclusion criteria. Reasons for being eligible but not enrolled were recorded. Once a Research Coordinator determined that a patient was eligible, they were approached for informed consent which was obtained either directly from the patient or their substitute decision maker. After obtaining informed consent, the Research Coordinator arranged for a CT scan to determine the CAC score. After the date of the CT scan results, the study drug had to be initiated within 4 weeks. This 4 week window provided sufficient time to arrange for the study treatment to be ordered, allocated, prepared, and dispensed. If the CAC score was < 30 AUs, the patient received a letter that explained that they were ineligible for the trial based on minimal or no calcium present in the arteries in their heart. The Principal Investigator's contact information was contained in the letter in the event that a patient had further questions. If the CAC score was ≥ 30 AUs, the Research Coordinator contacted their local hospital pharmacy. A designated research pharmacist or pharmacy technician accessed the secure web-based CRS and obtained the patient's treatment allocation. The research pharmacist or pharmacy technician then prepared the study medication according to the assigned treatment allocation. The blinded medication was transported to the dialysis unit for administration to the patient.

4.3 Sample Size Considerations

The original protocol sample size is quoted below:

The multicenter pilot study will enroll a total of 50 patients from 3 Canadian Centers and 1 US site. We will combine these data with 30 patients from the single-center iPACK-HD pilot study at Queen's University for a total sample size of 80 patients. Table 1 [in appendix B] describes the probability of meeting feasibility outcome 1 to 4 under a range of true population values. With 80 patients, the overall rate of CAC progression will have at least a 63% and 95% chance of being estimated within $\pm 5\%$ and $\pm 10\%$ of the true population value respectively. Therefore, the total pilot sample size (n=80) should be adequate to reliably assess the feasibility of the fully-powered multi-center study. We believe a total sample size of 30 patients from Queen's University and 50 patients from 3 Canadian sites and 1 US site for a total of 80 patients will be adequate to thoroughly pilot the trial procedures and obtain acceptably accurate estimates for the study outcomes. The pilot study will not be used to determine effect size but will provide further information regarding the distribution of our primary outcome that will allow us to further refine a definitive sample size estimate. We anticipate that, to optimally power the definitive Phase II study, we need approximately 430 patients.

Since the original protocol did not anticipate that we would perform any by-arm comparisons, these are not addressed in the above sample size consideration quoted from the pilot protocol. Without adjustment for covariates or multiplicity of outcomes, a sample size of 40 per arm would achieve 80% power at a two-sided $\alpha=0.05$ to compare means between groups using the two-sample t-test for approximately normal outcomes (regardless of equality of variance) if the population mean difference between arms was 63% of the within group standard deviation. If the Wilcoxon rank-sum test was used, we would achieve 80% power if the concordance index between the treatment arm and outcome value was 0.68. For binary outcomes (such as mortality or fracture), the sample size would achieve at least 80% power as long as the absolute difference in proportions between groups was 30%.

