5.2 Analysis Populations

All analyses will use a modified intent-to-treat population using all available data. However, one patient who developed an exclusion criteria post-randomization but did not receive any study intervention will be excluded from primary analysis. Thus, all randomized patients will be analyzed in the arm they were randomized to regardless of treatment compliance or data completion.

6 Trial Population

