7.1 Outcome Definitions

7.1.1 Feasibility Outcomes (Primary)

The pre-specified primary outcomes are as follows:

	Outcome	Definition	Target
1	Recruitment rate	Number of participants recruited per month at each site (total eligible randomized patients per site divided by date of last randomized patient at that site minus date of first randomized patient at that site, with month defined as 30.4 days. This will exclude first phase of KGH enrollment), as well as an overall crude average of each site’s rate.	>4.17 per month
2	Compliance with study medication	Proportion of prescribed doses received (divide received doses by prescribed for each patient to get a patient level measure before summarizing).	≥90% of prescribed
3	Dropout rate	Proportion of participants who dropped out from the trial (1-[% of randomized patients who either have a known date of death during the study period OR have a non-missing CAC value measured at least 6 months after randomization]).	<20%
4	Adherence to study protocol	Proportion of participants who adhered to the study protocol (90% study medication compliance and not dropped out) (all pooled).	≥80%
5	Rates of eligible patients consented and randomized	Proportion of eligible patients who were A) consented and B) randomized to the study.	No target

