7.1.2 Secondary Outcomes

- 1) Coronary artery calcification progression:
 - a) the percent and absolute change of the Agatston and volume calcium scores (CT scan) will be assessed at study exit vs. baseline. Included measures will be: Total CAC, Left Main CAC, Right Coronary Artery CAC, Left Anterior Descending CAC, Circumflex CAC, and Posterior Descending Artery CAC.
 - b) the proportion of participants with a 15% or greater increase in Agatston and volume calcium scores will be assessed at study exit vs baseline.
- 2) Coronary artery calcification regression: the proportion of participants with a 10% or greater decrease in Agatston and volume calcium scores will be assessed at study exit vs baseline.
- 3) Aortic valve calcification progression: the absolute and percentage change of the Agatston and volume calcium scores (CT scan) will be assessed at study exit vs. baseline.
- 4) Mitral valve calcification progression: the absolute and percentage change of the Agatston and volume calcium scores (CT scan) will be assessed at study exit vs. baseline.
- 5) AAC score: the AAC score (mean score in L1-L4, mean number of positive segments, mean total severity using lateral lumbar spine radiographs) will be assessed at study exit vs. baseline.
- 6) Biomarkers of vitamin K status: Gas6, PK, MK4, osteocalcin Gla, osteocalcin Glu, osteocalcin Gla to Glu ratio, percent of osteocalcin undercarboxylated, and dpucMGP will be assessed at baseline, four, eight and study exit. PIVKA-II will be assessed at baseline and study exit.
- 7) Thoracic vertebral fractures: The prevalence and incidence of thoracic vertebral fractures (anterior and lateral radiographs) will be assessed at baseline and study exit.
- 8) Lumbar vertebral fractures: The prevalence and incidence of lumbar vertebral fractures (anterior and lateral radiographs) will be assessed at baseline and study exit.
- 9) Events of clinical interest:

The presence or absence and total of the following events will be assessed across the study duration per patient:

 - i) Hospitalizations
 - ii) Cardiovascular events: acute coronary syndrome, congestive heart failure, stroke, transient ischemic attack, amputation, and cardiac (symptom-driven) (cerebral or peripheral) revascularization procedure, or cardiac arrest
 - iii) Thrombosis: deep vein thrombosis and pulmonary embolism
 - iv) HD access thrombosis. Fistula and/or graft thrombosis or dialysis catheter thrombosis
 - v) Mortality: all-cause and cardiovascular cause

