7.2 Analysis Methods

The feasibility outcomes will be presented descriptively overall as rates or proportions. In addition, compliance with study medication, dropout rate, and adherence to study protocol will be compared by arm. Reasons for loss-to-follow-up and non-compliance will be tabulated.

For the binary outcomes, we will provide counts and percentages by arm and compare arms by the Mantel-Haenszel test stratified by site and diabetes (or Fisher's Exact Test for outcomes with less than 20 events or non-events).

This study has many continuous outcomes that are far from normally distributed. For all continuous outcomes, we will report medians and quartiles by arm and compare arms by the Van Elteren test stratified by site and diabetes. Selected continuous variables may be depicted by clustered boxplots comparing the two arms over time. Biomarkers assessed at multiple time points will have both absolute value and change from baseline compared by arm at each time point.

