7.3 Missing Data

The number of missing items will be presented by arm for each outcome. Imputation will not be performed for this feasibility/phase II pilot study.

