8.2 Validation of SAS Database and Analysis

The study Principal Investigator and Project Leader will sense check all results to make sure they are not highly suspicious and that all counts are consistent with the patient flow diagram.

A second statistician who did not perform the primary analysis will independently verify the patient flow counts and re-analyze the main secondary outcome of CAC progression (measured by percent change in Agatston and percent change in the volume calcium scores), as well as the biomarkers of vitamin K status and inflammation.

9 References

10 Appendix A: Statistical Analysis Plan (SAP) Checklist v 1.0 2019

Section/Item	Index	Description	Reported on page #
Section 1: Administrative information			
Trial and Trial registration	1a	Descriptive title that matches the protocol, with SAP either as a forerunner or subtitle, and trial acronym (if applicable)	1
	1b	Trial registration number	1
SAP Version	2	SAP version number with dates	1
Protocol Version	3	Reference to version of protocol being used	1
SAP revisions	4a	SAP revision history	1
	4b	Justification for each SAP revision	N/A
	4c	Timing of SAP revisions in relation to interim analyses, etc.	1
Roles and responsibility	5	Names, affiliations, and roles of SAP contributors	1, 3
Signatures of:	6a	Person writing the SAP	2
	6b	Senior statistician responsible	2
	6c	Chief investigator/clinical lead	2
Section 2: Introduction			
Background and rationale	7	Synopsis of trial background and rationale including a brief description of research question and brief justification for undertaking the trial	6
Objectives	8	Description of specific objectives or hypotheses	6
Section 3: Study Methods			
Trial design	9	Brief description of trial design including type of trial (e.g., parallel group, multi-arm, crossover, factorial) and allocation ratio and may include brief description of interventions	7

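### SAP section 4.3 overstates a precision bound: with 80 patients the worst-case chance of estimating the CAC progression rate within ±10 points is about 93%, not at least 95%

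*SAP*

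**What the plan says.** Section 4.3 of the SAP (Sample Size Considerations) reproduces the sample size paragraph of the original protocol. On the precision of the pooled CAC progression rate it takes two limits around the true value, ±5% and ±10%, and states: "With 80 patients, the overall rate of CAC progression will have at least a 63% and 95% chance of being estimated within" them. The following sentence draws the inference that 80 patients should be adequate to assess feasibility reliably.

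Section 4.3 gives no progression rate, and the part of Appendix B that is shown does not deal with CAC progression. Section 7.1.2 defines the binary measure as "the proportion of participants with a 15% or greater increase in Agatston and volume calcium scores will be assessed at study exit" against baseline. Section 8.2 describes the second statistician's task as to "re-analyze the main secondary outcome of CAC progression", so CAC progression is the leading efficacy outcome of the trial, although section 8.2 defines it there by percent change.

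**The concern.** A probability given as *at least* some value, with no true rate attached, is a claim about every possible rate. The sampling variance of a proportion is largest at 50%, so the claim stands or falls near that rate. The two printed figures should therefore come from one method at its worst case. They do not: the calculation that returns 63% for ±5 points returns a figure below 95% for ±10 points.

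What is at stake is modest. A reader would take the progression rate to be slightly more precise than the design makes it. The section also says that the pilot will inform the distribution of the outcome and a refined sample size for the definitive trial, so the stated precision of this rate ought to be right.

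**Working it through.** **Inputs.** n = 80 and the stated pair, 63% and 95%, come from section 4.3. The limits ±5% and ±10% are read as percentage points. The true rate p is not given, so p = 0.5 is taken as the worst case and other values are shown below.

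**Reproducing the plan's first figure (normal approximation).** The chance that the estimate falls within ±m of p is 2Φ(m / √(p(1−p)/n)) − 1.

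- Standard error at p = 0.5: √(0.25/80) = 0.0559.
- m = 0.05: 0.05/0.0559 = 0.894, giving 62.9%. This matches the printed 63%.
- m = 0.10: 0.10/0.0559 = 1.789, giving 92.6%. The printed figure is 95%, a shortfall of 95 − 92.6 = 2.4 points.

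**Exact binomial, n = 80.** The probability that |X/80 − p| ≤ m was summed directly and minimised over a fine grid of p.

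| Method | Within ±5 | Within ±10 |
|---|---|---|
| Stated in section 4.3 | at least 63% | at least 95% |
| Normal approximation, p = 0.5 | 62.9% | 92.6% |
| Exact, limits included, minimum over p | 62.6% | 92.5% |
| Exact, limits included, exactly p = 0.5 | 68.6% | 94.3% |
| Exact, strict limits, p = 0.5 (its minimum) | 56.6% | 90.7% |
| Exact, strict limits, p = 0.25 or 0.75 | 63.4% | 94.8% |

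The second and third rows agree on a worst-case pair of about 63% and 93%. The exact value at precisely 50% is higher because both limits then fall on attainable counts (32 and 48 of 80 for ±10 points). For rates just off 50% it drops to the minimum shown. Only the last row comes close to the printed pair. It needs a rate that section 4.3 does not state, and with strict limits the same method falls to 56.6% and 90.7% at 50%, so the pair would not be a lower bound.

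**Where 95% within ±10 points does hold (normal approximation).** Setting 0.10/√(p(1−p)/80) = 1.96 gives p(1−p) = 80 × (0.10/1.96)² = 0.208, so p = 0.296 or 0.704. Values by rate:

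- p = 0.40: 93.2%
- p = 0.35: 93.9%
- p = 0.30: 94.9%
- p = 0.25: 96.1%

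**Sample size that would support the statement at p = 0.5.** n = 0.25 × (1.96/0.10)² = 96.04, or about 96 patients against 80.

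**The case against.** The case for leaving the text alone has four parts.

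- **It is a quotation.** The SAP reproduces protocol text and does not make this calculation itself, and enrolment is over, so nothing can be resized. This is true, and it is the reason to annotate the sentence and not rewrite it. It does not make the bound correct.
- **The gap is small.** At round rates the exact probability with limits included is near the printed figure: 95.4% or 95.5% at 35%, depending on rounding (0.9545), 94.8% at 40% and 94.3% at 50%. That stands as a measure of size. But the same method gives about 69% to 71% for ±5 points at these rates, so it does not yield the printed pair, and 94.3% is still below 95%.
- **The protocol may give a rate.** The protocol is not shown, and a rate could be stated there. This cannot be excluded, and the fix allows for it. A stated rate would, however, make the sentence conditional, whereas it is worded as a bound.
- **Nothing depends on it.** The adequacy statement also rests on the feasibility probabilities in Appendix B, which this point does not touch, and 93% would hardly have changed the conclusion. That is accepted, and it sets the severity.

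A reader might go further and infer that the by-arm power figures in the same section are also wrong, because scans will be missing: section 5.2 removes one randomized patient, section 7.1.1 counts a patient who died without an exit scan as retained, and section 7.3 rules out imputation. The document does not support that inference. The power statement is expressly conditional: "a sample size of 40 per arm would achieve 80% power at a two-sided" α of 0.05. At that number the 0.63 SD difference gives 79.5% power and the concordance of 0.68 gives 79.6%, which agree with 80% within rounding. The n in such a statement is by convention the number analysed. Sections 6.3 and 7.3 already provide for reporting the numbers analysed and missing by arm, and the SAP text available does not give the number scanned, so any lower power figure would be hypothetical.

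**Conclusion.** The point holds for the precision statement only. Read as a bound over all true rates, the pair in section 4.3 should be about 63% and 93%. The ±10-point figure is overstated by about 2.4 percentage points (92.6% by the normal approximation; 92.5% as the exact minimum with limits included).

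This rests on three assumptions: ±5% and ±10% are percentage points, all 80 patients contribute to the rate, and *at least* is meant without a restriction on the rate. If the authors had in mind a rate of about 30% or lower, or 70% or higher, 95% within ±10 points is defensible by the normal approximation, but the text must then say so.

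Severity is low. The figure enters no test, feasibility target or decision rule. The by-arm power figures are not part of the finding.

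**What to change.** Leave the protocol quotation as it is and add one SAP note directly after it, in either of two forms:

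- With 80 patients, the chance of estimating the progression rate within ±10 percentage points is about 93% in the worst case (true rate near 50%), and reaches 95% by the normal approximation for true rates of about 30% or lower, or 70% or higher.
- If the 95% was calculated for a particular progression rate, state that rate and the method used (normal or exact, limits included or not), and make clear that the figure applies under that assumption and is not a general lower bound.

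The by-arm power paragraph and Appendix B need no change on this account. The cost is a sentence or two of SAP wording and a slightly less favourable precision figure. No patients, analyses or timelines are affected.
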